9.0 Blinding and Unblinding (Masking and Unmasking)

The student interviewer/data entry assistant will be blinded on who is chosen by random for the intervention group and will not know whose information belongs to whom.

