All AEs, not otherwise precluded per the protocol, will be captured on the appropriate reportable event or case report form (CRF) as provided by the University of Iowa Institutional Review Board in an online form. Information to be collected includes event description, time of onset, clinician's assessment of severity, relationship to study procedures (assessed only by those with the training and authority to make a diagnosis), and time of resolution/stabilization of the event. All AEs occurring while on study will be documented appropriately regardless of relationship to the study. All AEs will be followed to adequate resolution.

Any medical or psychiatric condition that is present at the time that the participant is screened will be considered as baseline and not reported as an AE. However, if the study participant's condition deteriorates at any time during the study, it will be recorded as an AE.

Changes in the severity of an AE will be documented to allow an assessment of the duration of the event at each level of severity to be performed. After each interview, the GAD-7 anxiety score will be calculated within two weeks of administration to identify participants experiencing elevated levels of symptoms. In addition, during each intervention encounter, the interventionist will ask the participant "Have you noticed anything different since you started the study?" Documentation of onset and duration of each episode will be maintained for AEs characterized as intermittent. *See Appendices I for OC-HE documentation and J for AEs/SAEs Listing.*

The PI or Project Manager will record events with start dates occurring any time after informed consent is obtained until 7 (for non-serious AEs) or 30 days (for SAEs) after the last day of study participation. At each study visit, the staff will inquire about the occurrence of AE/SAEs since the last visit. Events will be followed for outcome information until resolution or stabilization.

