12.2 Study Forms

Form Name	When Given	When Collected	Appendix	Maintenance
Eligibility Screening	Read to potential participant by RA	Before potential participant receiving any materials	B	Kept in Participant Folder locked in [name]'s office
Study Flyer	In Research Packet after participant screens eligible	N/A	D	N/A
Study Summary	In Research Packet after participant screens eligible	N/A	E	N/A
Consent Letter	In Research Packet after participant screens eligible. Read through with Interviewer before baseline and revisited before 3 and 6 month follow up	N/A	F	N/A
Participant Contact Form	Given by clinicians when a potential participant appears to be eligible	At PWD appointment by clinicians, given to research manager	U	Kept in Participant Folder locked in [name]'s office

	(Research Manager will do eligibility screening)			
Reimbursement Form	Directly after baseline, 3 month follow-up, 6 month follow-up	Directly after baseline, 3 month follow-up, 6 month follow-up	N	Kept in Participant Folder locked in [name]'s office

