12.5 Administrative Forms

Form	Appendix	Description
Participant Identification Code List	R	Used to document the participant's study identification number, name, and other identifying information. Stored separately from research records since it is the link between a study ID and participant's name.
Recruitment Log	C	Used to list participants screened; includes those who fail screening and those who are enrolled. Collects date, age, gender, race, care needs, relationship to PWD, Rural (Y/N), Agreed to participate, Reason for not enrolling, study ID
Phone Call Log	S	Used to log all phone call conversations/follow-ups
Study Personnel	T	Used to list contact information for all study personnel and their specific responsibilities
Heritage AAA Log		Used by the OC, who is an employee at Heritage Area Agency on Aging to log options counseling sessions
Research Log		Extensive Database with points of contact to track participants through the research process
Intervention Log		Database at University of Iowa where the OC-HE tracks options counseling sessions
EPIC		University of Iowa Electronic Medical Record where Care Plans will be uploaded or typed into the "notes"

		section
Participant Contact Form (from Clinic to Research Staff)	U	Used by clinicians to collect contact information about the potential participants so that the Research Manager can contact the interested potential participant
Participant Reimbursement Form	N	Used by the Interviewer to collect information about the participant so that the participant can be paid their \$20 incentive for each interview
Interview Script	V	Used by the interviewer to introduce the study, ask about adverse events, conduct the interview, and end the interview
Adverse Event Form	G	Used by the PI to report Adverse Events
Serious Adverse Event Form	H	Used by the PI to report Serious Adverse Events

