15.0 Data and Safety Monitoring Activities

Given the nature of this study, single-site minimal risk trial, the [name] (PI) will be responsible for ensuring participants' safety on a daily basis. The Data and Safety Monitoring Board (DSMB) will act in an advisory capacity to monitor participant safety, evaluate the progress of the study, to review procedures for maintaining the confidentiality of data, the quality of data collection, management, and analysis.

The PI will meet with the research team weekly to conduct ongoing data and safety monitoring, and will meet bi-annually with the Data Safety Monitoring Board (DSMB) consisting of three external board members, Drs. [name], [name], and [name]. The PI will be informed of serious adverse events (SAEs) as soon as they occur and will notify the UI IRB and NIA within 24 hours of notification.

The DSMB will hold a minimum of two web-based conference calls per year (about two hours per call) to discuss protocols, progress of the intervention and research activities, and data and participant safety. The PI will prepare a Safety Report to be circulated prior to the scheduled call for DSMB members to review. The reports will contain information and analyses of study procedures, progress, and data and safety issues. The board members will review the study protocol and information presented in the report and will provide recommendations on recruitment, retention, quality control, and safety procedures while ensuring the confidentiality of the study participants and results. Through these activities, we will ensure that all

protocols are conducted in compliance with the AE and SAE guidelines and reports are sent to appropriate individuals including the University of Iowa IRB and the Program Officer at the NIH.

The content of the data and safety monitoring report will include: a brief summary of study organization, purpose and procedures, overall study status, participant enrollment and retention, reasons for non-participation, aggregated descriptive information of the participants, changes to study protocol, quality of collected data, status of data management, incidence of ADs/SAEs/unexpected problems and actions taken, and updated study timeline. The design of this study does not involve masking.

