Thank you for participating in our study. We would like to ask you some questions about your experiences supporting individuals diagnosed with dementia, how you are feeling in general, about clinical or community-based services that are available, as well as some background information about you and the person who received dementia diagnosis who we refer to as “the individual” in this survey. I’m going to start with questions about your background.

Conduct Baseline Interview

After Baseline:

Thank you for taking the time to speak with me today and answer these questions. I will be sending you \$20.00 in the mail and providing a follow up call to make sure you received the money.

If participant decided not to participate:

That's ok. For our records may I ask you why you decided not to participate?

Research Assistant Script 3: 3 Month Follow-up Survey

Interviewer calls to do 3 month follow-up

Hi this is _____ at the University of Iowa College of Public Health. I am calling/here to do to do the 3 month follow-up survey for the Building a Bridge project with _____.

Before we get started, I just wanted to check and see how you are doing. Have you noticed anything different since you started the study? *If any adverse events, create an AE form and fill out.*

Thank you for participating in our study. We would like to ask you some questions about your experiences supporting individuals diagnosed with dementia, how you are feeling in general, about clinical or community-based services that are available, as well as some background information about you and the person who received dementia diagnosis who we refer to as “the individual” in this survey. I’m going to start with questions about your background.

Conduct 3 month follow-up survey

After Interview:

Thank you for taking the time to speak with me today and answer these questions. I will be sending you \$20.00 in the mail and providing a follow up call to make sure you received the money.

If participant decided not to participate:

That's ok. For our records may I ask you why you decided not to participate?

Research Assistant Script 4: 6 Month Follow-up Survey

Interviewer calls to do 6 month follow-up

Hi this is _____ at the University of Iowa College of Public Health. I am calling/here to do to do the 6 month follow-up survey for the Building a Bridge project with _____.

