Before we get started, I just wanted to check and see how you are doing. Have you noticed anything different since you started the study? *If any adverse events, create an AE form and fill out.*

Thank you for participating in our study. We would like to ask you some questions about your experiences supporting individuals diagnosed with dementia, how you are feeling in general, about clinical or community-based services that are available, as well as some background information about you and the person who received dementia diagnosis who we refer to as “the individual” in this survey. I’m going to start with questions about your background.

Conduct 6 month follow-up survey

After Interview:

Thank you for taking the time to speak with me today and answer these questions. I will be sending you \$20.00 in the mail and providing a follow up call to make sure you received the money.

Thank you for participating in this study. Your participation is now complete. You can contact me at _____ if you have any further questions. You will receive your \$20 reimbursement and a letter that will let you know how you can find the results of this study and who to contact with further questions.

If participant decided not to participate:

That's ok. For our records may I ask you why you decided not to participate?

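### An open adverse-event question before the 3- and 6-month surveys may reveal allocation to the interviewer whom the protocol calls blinded

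*Protocol*

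**What the plan says.** - **Blinding.** Protocol section 9.0: "The student interviewer/data entry assistant will be blinded on who is chosen by random for the intervention group". Section 15.0, on data and safety monitoring, says the opposite: "The design of this study does not involve masking".
- **Scripts.** In Appendix V, the 3-month script (Script 3) and the 6-month script (Script 4) both begin "Before we get started, I just wanted to check and see how you are doing" and then ask "Have you noticed anything different since you started the study". The only instruction attached is to complete an adverse-event form if one is needed. The survey follows.
- **Order.** Section 12.5 describes the interview script in the same sequence: "Used by the interviewer to introduce the study, ask about adverse events, conduct the interview, and end the interview".
- **Purpose.** Section 10.0 has staff ask at each study visit about adverse events since the previous visit, and defines an adverse event as an untoward medical occurrence. The same section gives the interventionist the identical sentence: "during each intervention encounter, the interventionist will ask the participant".
- **Outcomes.** Caregiver burden is one of the two outcomes in the primary objective (section 1.0). Section 5.0 says assessments rest on the participants' own reports. Script 1 in Appendix V has the interviewer give all three surveys in person or by phone.

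**The concern.** Caregivers know their own arm, so blinding cannot remove their reporting bias. What section 9.0 can limit is the interviewer's contribution: differences in probing, tone and coding between arms. That protection lasts only while the interviewer does not know the arm.

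The question is open, is not restricted to health, and refers to the period since joining the study. For an OC-HE caregiver, the main thing the study has added is a counselor, a care plan and education modules (section 7.0), so naming them is a foreseeable answer. A control caregiver has no such contacts to mention. The exchange comes before any survey item at both follow-up waves, so it could affect every retained participant, about 40 per group on the protocol's own attrition assumption.

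**Working it through.** **1. Position.** In Scripts 3 and 4 the sequence is: greeting, open question, adverse-event form if needed, introduction, survey. Section 12.5 confirms it. Nothing in the supplied scripts asks the caregiver to withhold the group, gives the check to another person, or provides for recording an unblinding.

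**2. Wording against purpose.** Section 10.0 needs untoward medical occurrences since the last visit. The script asks for any difference since the study began. It is therefore broader in content, and at 6 months it covers a longer window than section 10.0 sets. A health-focused question would fit section 10.0 better and would invite less talk about the programme.

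**3. Other routes to the same disclosure.** Section 12.4 has the interviewer at weekly meetings with the interventionist. Section 5.0 lists service use and knowledge, social support and networks among the survey topics. The SAP (network composition and perceived support) has caregivers add new supporters at 3 and 6 months and counts professional providers. A full answer to these items can name the counselor. The open question is thus one route of several, and its separate effect cannot be isolated.

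**4. Scale, for illustration only.**

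Inputs from section 5.0: 106 enrolled, 25% attrition, 40 per group, a 4-point difference, about 84% power. Attrition check: 106 × 0.75 = 79.5, in line with the stated 80.

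The SD, alpha, sidedness and repeated-measures correlation are not given, so the 84% cannot be reproduced. It can only be inverted. Assuming a simple two-sample comparison at two-sided 5%:

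- SD = 4 / [√(2/40) × (1.960 + 0.994)] = 4 / (0.2236 × 2.954) ≈ 6.05
- SE = 6.05 × 0.2236 ≈ 1.354

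With no true effect and a systematic between-arm shift b, the rejection probability is P(|Z + b/SE| > 1.96):

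| Assumed shift b (points) | b/SE | False-positive rate |
|---|---|---|
| 0.5 | 0.37 | 6.6% |
| 1 | 0.74 | 11.4% |
| 2 | 1.48 | 31.5% |

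Using the t distribution to back-solve gives SD 5.98 and 6.6%, 11.6% and 32.1%. If the design were one-sided at 5%, the implied SD would be 6.78 and the rates 9.4%, 16.2% and 37.3%. A 1-point shift is 1/4 = 25% of the target difference.

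The documents give no value for b. The table shows how sensitive the comparison would be to a shift of a given size, whatever its cause. It does not estimate what this question produces.

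**The case against.** The strongest reply is that section 15.0 says there is no masking, so there is no blind to protect. That conflict is real and has to be settled. Section 9.0 is, however, the section written for the purpose. If it stands, the scripts work against it. If section 15.0 stands, assessment cannot be reported as blinded.

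A second reply is that the survey content and the weekly meetings can unblind the interviewer anyway. This stands in part: changing the scripts will not secure the blind. It is no reason to keep a scripted route that costs almost nothing to close.

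Third, the question is a safety check, follows an enquiry about how the caregiver is, and carries an adverse-event instruction, so many caregivers may answer about health alone. That is fair. The documents support that allocation may be disclosed, no more.

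A reader might infer more, in four ways that the text does not support:

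- **That the interview itself breaks the blind.** No source shows how caregivers answer, or that OC-HE caregivers have learned to answer this sentence about the programme.
- **That burden is rated straight after the question.** Both scripts say the survey begins with background items, and the instrument is not in the text supplied.
- **That the interviewer's blind is the only safeguard.** Sections 12.3 and 13.2 provide interviewer training, recorded sessions, re-entry of 20% of interviews and manager attendance at 10%. These are partial, since re-entry tests data entry and attendance tests the consent reading, but they exist.
- **That the consent letter is a second leak.** Section 12.2 has it "revisited before 3 and 6 month follow up", but the letter is given before randomization, section 6.0 mentions only offering a new copy, and Scripts 3 and 4 contain no reading of it.

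**Conclusion.** The point holds as a procedural weakness worth correcting. An interviewer described as blinded is scripted to ask, before the outcome survey, an open question whose answer may disclose the arm. It applies at both follow-up waves.

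The conclusion rests on section 9.0 expressing the intended design and on burden being collected within these interviews. It does not rest on the illustrative error rates. The size of any bias is unknown, and a direction favouring OC-HE is plausible but not documented. The other primary outcome, emergency care, is likely to be less exposed, because section 6.1 says use of medical services is taken from the medical record.

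**What to change.** 1. **Move the check.** In Scripts 3 and 4, place the adverse-event check at the end of the contact. Require it before any call or visit closes, including one that stops early, because section 5.0 anticipates partly completed interviews.
2. **Narrow the wording.** Ask about new or worse physical or emotional health problems, or hospital or emergency visits, since the last visit. This matches section 10.0.
3. **Open with a limited request**, for example: *Please do not tell me which study group you are in; answer each survey question fully, including about people and services that help you.* A ban on mentioning programme contacts would be wrong, because the service and network items need those answers.
4. **Order the survey.** Where the instrument allows, ask the burden items before the service and network items.
5. **Reconcile sections 9.0 and 15.0** on whether the interviewer is masked.

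The cost is an edit to two scripts and possibly a change in item order, with no extra staff or contacts. Adverse events would be recorded later in the same contact, by the 30 to 50 minutes that Appendix V gives for a survey. The blind would be better protected but not secured.

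The SAP is dated January 2022 and the protocol planned to finish data collection by March 2021. If follow-up is already complete, the remedy is in reporting: do not describe outcome assessment as blinded without stating this limitation.

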APPENDIX W
Evaluation to Sign an Informed Consent Document for Research
[DeRenzo EG, et al. J Health Care Law Polic 1998;1:66-87]

Subject Identifier: _____

Date of Evaluation: _____

Directions

Make a subjective judgment regarding item 1. Ask the subject questions 2-5 and record responses. The evaluator may use different wording in asking the questions in order to assist the subject's understanding.

1. Is the subject alert and able to communicate with the examiner? Yes _____ No _____
2. Ask the subject to name at least two potential risks of participating in the study.

3. Ask the subject to name at least two things that he/she will be expected to do during the study.

4. Ask the subject to explain what he/she would do if he/she no longer wanted to participate in the study.

5. Ask the subject to explain what he/she would do if he/she experienced distress or discomfort during the study.

Evaluator's Signature

It is my opinion that the subject is alert, able to communicate, and gave acceptable answers to the questions above.

Evaluator's Signature

Date

APPENDIX X – MOP MODIFICATION LOG

Section #	Version #	Page #	Text Location	Modification Summary

Building a Bridge (between clinical and community care): Post-diagnosis support for persons with dementia and their families

Grant Number: 1R21AG056716-01A1

National Clinical Trial (NCT) Identified Number: NCT03932812

Principal Investigator: [name]

Sponsor: University of Iowa College of Public Health

Funded by: National Institute on Aging (NIA)

Revised Analytic Plan

[figure not shown]
January 2022

Building a Bridge Data Analyses Plan

Overview of the Intervention. Building a Bridge: a post-diagnosis support of persons with dementia and their family aims to assist community dwelling individuals newly diagnosed with dementia and their families to prepare them for community-based care and connect them to the services provided by the local Area Agency on Aging. The intervention consists of two components, Options Counseling (OC) and Health Education (HE) – the OC-HE intervention. Families receive standard OC services provided through the Iowa's Area Agencies on Aging that include a family assessment, counseling and provision of emotional support, access to community resources and supports, and development of independent-living plans (family action plans). The HE component involves the provision of post-diagnosis education using the educational modules specifically developed for this project to address the needs of families who recently received the diagnosis. The intervention contains 8 modules to support successful role transitions for patients and family: overview of dementia (e.g., symptoms, stages, management, things to consider after diagnosis), anticipating changes and challenges, social relationships and daily life, interacting with providers, addressing future needs, dementia and driving, elder mistreatment, and pandemic-related challenges. The module on social relationships and interactions focus on enhancing social support through the discussion of strategies to elicit positive support from network members.

Interventions are ongoing and flexible to meet the needs of the individual family. Following the standard OC protocol, the family receives an initial telephone intervention (previously in-person home visit, but occurred over the phone due to the pandemic) by the interventionist. During the initial call, the OC uses assessment tool to identify caregiver/family needs and develop family action plans to connect families directly to services and programs available in the area. The interventionist also conducts an assessment to determine educational needs, then conducts 2 additional monthly follow-up calls to adjust the care plans and to provide educational components appropriate at each point (3-month intervention). This program, thus, creates direct links between the medical clinics, HCBS, and family. The OC tailors the information provision to meet the needs of those receiving it by providing additional information as the time progresses, allowing the recipients to identify their concerns at the moment and presenting materials to address expressed concerns. Participants receive all educational materials and a brief overview of contents at the end of the 3-months intervention period, including the topics that may not have been covered in great detail during the intervention calls. The Area Agency on Aging provides continued support to individuals who need their services after the completion of the intervention.

Mechanisms of Influence. The social network framework highlights the importance of enhancing network functions (e.g., social support) on health outcomes. Strong social support networks have been shown to be important for the well-being of caregivers and care recipients, and their ability to remain in the community. The intervention provides families 1) tangible, informational, and emotional support, 2) guidance on building strong support systems and effective communication, and 3) access service linking families directly to community-based resources. Through these activities, we intend to strengthen families' social networks to facilitate successful community living. In our prior study, families considered formal providers as important members of their caregiving support systems, suggesting the important role Area Agency on Aging staff can play in this mechanism. In this study, we are systematically examining the compositional and functional characteristics of social networks, that are theorized to influence patient and family outcomes. We will assess the mechanisms of influence using the social network measures specifically developed for dementia caregiving studies that assess social interactions specific to caregiving in addition to general support. Understanding the mechanisms through which intervention improves outcomes will provide a framework to optimize support for patients and their families across all stages of the illness.

Revised Data Analysis Plan

Network composition: Network members are enumerated based on participation in caregiving activities and provision of support to caregivers at baseline. In 3- and 6-month assessments, participants indicate changes in their networks (e.g., indicate those who are no longer part of support network, add new support providers). We will develop network composition measures including network size and proportion/number of family, non-family/friends, professional providers, live locally, gender, age groups (e.g., same/older/younger generations).

Perceived support: At each assessment, the participants report their relationships with each network member (e.g., who provides emotional support? Who helps you provide direct care? Who participates in discussions to make care decisions) to assess network functions. Levels of support can be determined by taking an average support levels among family, non-family, professionals, for each type of support (e.g., emotional, informational, instrumental, direct care, care decision making).

Social engagement: Participants identify network members with whom they engage in social activities to assess how the network functions as a context for social engagement.

At the patient level, generalized linear models (GLM) with an appropriate link function (e.g., the identical link for continuous outcomes, the logit for dichotomous outcome, and the log link for count outcomes) will be used to assess associations between the caregiver and patient outcomes and network composition and network functions. In particular, a set of the composition measures will be considered as independent variables to each outcome in a GLM. Similarly, a set of network functions (e.g., change between baseline and 3-month) will be included to assess the association with each outcome at 6-month in a GLM.

Follow-up analyses

Once we identify network functions that are important for the caregiver and patient outcomes (e.g., emotional support, provision of direct care support) are identified in the main analyses, we will be able to conduct dyad-level analyses to identify the whole network characteristics (e.g., network size, homogeneity), network member characteristics (e.g., gender, relationships, live locally), as well as relationship characteristics (e.g., presence of trust, duration of relationship) that may contribute to such positive network functions.

At the dyadic-level, a logistic regression model will be fitted for each outcome (e.g., presence of emotional support, provision of direct care support) using generalized estimating equations with the exchangeable correlation structure to account for the clustering of the network members within the respondents' networks. Both respondent-level (e.g., gender, relationship to care recipient) and network member-level covariates (e.g., family member of the care recipient, age, whether living locally) will be considered in these models. To assess the impact of changes in network functions, differences between baseline and 3-month network functions (e.g., change in support provision) will be used as independent variables to the outcomes at 6-months.
